7.1. Subject Enrollment Procedures

Subjects will be recruited by various methods, including advertising, physician referral, brochures posted in health-care facilities, and subject databases.

Prior to screening a patient, each institution must have submitted all necessary regulatory documentation to Ozmosis Research Inc. Access to the electronic case report forms (eCRFs) will only be granted once this has been received. All sites should contact Ozmosis Research Inc. at the information provided on the cover page to verify study availability.

All subjects will provide written informed consent for the study at the beginning of the Screening Visit, prior to performance of any of the study procedures and collection of study data. Subjects will be assigned a unique subject number when the signing the informed consent.

A subject's eligibility for randomization will be determined at Visit 2 according to the inclusion and exclusion criteria set forth in [Section 10.1](#). Failure to meet specific inclusion or exclusion criteria will be reviewed on a case-by-case basis, and enrollment waivers will be completed as necessary. The sponsor must agree to any waivers prior to patient being randomized.

Upon enrollment into the study, an RTSM system will be used to assign patient to a treatment arm, according to the randomized treatment list. The system will assign a wallet number to the patient based upon treatment arm. Patients will be assigned the first wallet at Visit 2, a second wallet at Visit 4, and 2 additional wallets at Visit 6 (all in the same treatment arm)

Protocol treatment should begin within 17 working day of patient registration.

Note: it is the responsibility of the investigator in charge to satisfy themselves that the patient is indeed eligible before requesting registration.

7.1.1. Demographic Data and Medical History

The subject's demographic information and medical history will be recorded at the Screening Visit and documented on the appropriate CRF. This will include:

- Demographic information: sex, age, race and ethnicity
- Medical history for the past 10 years prior to screening and other relevant history will be collected, including other types of pain (e.g., arthritis); surgeries; diabetes; cancer; cardiovascular events; and gastrointestinal problems
- History of chronic widespread musculoskeletal nociceptive pain

7.1.2. Prior Medications

Prior and Concomitant Medications: Medications taken for the past 3 months preceding screening will be recorded at the Screening Visit (Visit 1). Prior medications include analgesics of all types, anti-inflammatory drugs, antidepressants, and anticonvulsants. Patient will be allowed to continue their current pain medication regimen as long as they are not taking a prohibited medication listed in Section 8.2.2. In addition, they should not start any other analgesics while in the study.

7.1.3. Treatment Assignment/Randomization and Blinding

At the Screening Visit (Visit 1), subjects who meet all entry criteria, including minimum pain score will be trained on completing the App entries and will enter the Baseline Period if the results of the laboratory tests confirm their eligibility. During this period, subjects will capture their 0-10 NPRS scores daily using the App. At Visit 2, App entries will be reviewed and those subjects who have an average daily pain intensity score ≥ 4.0 and ≤ 9.0 on the 0-10 NRS over the 1-week Baseline Period will be randomized to either FSD201 or placebo treatment in a double-blind manner; subjects will be required to have completed at least 5 of the daily diaries during the Baseline Period.

Randomization

Eligible patients who consent to participate in the trial will be randomized through the RTSM using a randomization list in a 2:1 manner with FSD201 or placebo.

Blinding

The investigators, site staff, monitor and sponsor will be blinded to the study assignment.

Unblinding

The study investigators, statistical team, and sponsor will be blinded to the trial randomization code. The Principal Investigator may decide to unblind a subject's treatment code in the case of a medical emergency or in the event of a serious medical condition, for which the knowledge of the treatment is essential for the clinical management of the subject's condition. The investigator should promptly document and explain to the Sponsor any premature unblinding (e.g. accidental unblinding, unblinding due to a serious adverse event, etc.) of the study participant. Women who become pregnant during the study period and male subjects whose partner becomes pregnant will be withdrawn from the study and unblinded due to unknown risks to the fetus. A subject's treatment may also be unblinded in the event of a suspected unexpected serious adverse event (SUSAR) in order to determine reportability of the event to regulatory authorities. Whenever possible, the Sponsor will be notified prior to breaking the blind.

When study participant unblinding is required, the investigator will use the RTSM system to determine treatment arm. Only the PI will have this function available. Unblinding will be documented in the Investigator site file (ISF) and the CRF. Unblinding the treatment assignment for the study will occur after database lock when all trial subjects have completed their end-of-treatment or study discontinuation visit.

Treatment

Investigational product (FSD201 or placebo) will be dispensed at Visit 2 (one wallet containing 15 days treatment), Visit 4 (one wallet containing 15 days treatment), and Visit 6 (2 wallets for a total of 28 days treatment). Outside of the visits, subjects are to orally self-administer the investigational product *b.i.d.* at home during the Treatment Period. The last dose of investigational product is to be taken in the morning of Visit 10. The investigational product is to be taken with a glass of water, within 30 minutes of a meal/food.

Subjects who forget to take their dose at the usual required time should take it immediately upon noting that it was missed. If a dose is missed altogether, the subject should record this in the daily dose compliance tracker (App) and continue with the normal scheduled dose on the following dose.

Adherence to Treatment: Following App review the Investigator or Investigator's designee will determine adherence to treatment. Subjects will be asked to bring their medication at Visit 4 and Visit 6 for an investigational product count. Subjects who missed >20% of the doses will be considered non-compliant. Non-compliant subjects will be counselled to adhere to the medication regimen and will be used for a sub-analysis study.

Safety Measures

General Physical Examination: A general physical assessment of the major body systems will be performed at the Screening Visit (Visit 1). An abbreviated physical exam focusing on the previously identified abnormalities or any patient reported symptoms will be performed at Visit 2, Visit 4, Visit 6, Visit 10 and the Early Termination Visit(if applicable).

Pregnancy Test (if applicable): At the Screening Visit, a serum pregnancy test will be performed. At Visit 2, Visit 4, Visit 6, Visit 10, and Early Termination a urine pregnancy test will be conducted at the clinic.

Vital Signs: Sitting blood pressure, heart rate, body temperature, oxygen saturation using Pulse oximetry and breathing rate will be measured at each visit after the subject has been sitting quietly for at least 5 minutes. Data will be recorded in the appropriate CRF.

Clinical Laboratory (Non fasting): Clinical laboratory testing will be performed at the Screening Visit (to determine and confirm eligibility) Visit 2, Visit 4, Visit 6, Visit 10 (End of Treatment) and in the event of Early Termination as shown in Table 2. Blood (~15 mL) and urine samples will be collected. The clinical laboratory analyses will include:

- Biochemistry: LFTs (serum ALT, AST, alkaline phosphatase, γ -glutamyl transpeptidase (GGT), albumin, bilirubin), CK, Cr (eGFR), blood urea nitrogen (BUN), HbA1c, lipid assessment, sodium, potassium, chloride, bicarbonate, and glucose

- Viral testing: HBV (antibody and antigen), HCV (antibody), HIV (antibody)
- Hematology: CBC with differential, PT/ INR, PTT
- Urinalysis: total urinalysis (chemical), drug test, Albumin/Cr ratio, urine pregnancy test including a microscopic examination
- Biomarkers: CRP, tryptase, cytokine panel (IL-1 beta, IL-2, IL-4, IL-6, IL-8, IL-10, IL-12 (p70), IL-13, TNF- α and IFN- γ) (only serum tryptase performed at Visit 1, all biomarkers performed at subsequent visits)

	Visit 1	Visit 2	Visit 4	Visit 6	Visit 10	Early Termination
	Screening	Day 0	Day 14	Day 28	Day 56	
Hematology						
CBC with differential	X	X	X	X	X	X
PT/ INR	X	X	X	X	X	X
PTT	X	X	X	X	X	X
Biochemistry						
HCV and HBV testing	X					
HIV testing	X					
Sodium	X	X	X	X	X	X
Potassium	X	X	X	X	X	X
Chloride	X	X	X	X	X	X
Bicarbonate	X	X	X	X	X	X
LFT (ALT, AST, GGT, ALP, albumin, bilirubin)	X	X	X	X	X	X
CK	X	X	X	X	X	X
Albumin/ Creatinine ratio	X	X	X	X	X	X
Creatinine (eGFR)	X	X	X	X	X	X
Blood urea nitrogen (BUN)	X	X	X	X	X	X
Glucose	X	X	X	X	X	X
HbA1C	X	X	X	X	X	X
Lipid assessment	X	X	X	X	X	X
beta-HCG (serum pregnancy)	X					
Biomarkers						
CRP		X	X	X	X	X
Serum Tryptase	X	X	X	X	X	X
Cytokine Panel*		X	X	X	X	X
FSD201 Exposure						
FSD201 Plasma Level		X	X	X	X	X
Urine Analysis						
Drug Test	X	X	X	X	X	X
Urine Pregnancy Test		X	X	X	X	X
Urinalysis (chemical)	X	X	X	X	X	X

Table 2 Lab Requirements

* IL-1 beta, IL-2, IL-4, IL-6, IL-8, IL-10, IL-12 (p70), IL-13, TNF- α -and IFN gamma.

A central lab will be used for analysis in this study. Data will be recorded in the appropriate CRF. Laboratory data may be repeated at the discretion of the Investigator.

Adverse Events (AE): At Visit 2, subjects will be instructed to call the study center in the event of any AEs that may require medical attention, regardless of possible relatedness to the study medication. At each visit and during the telephone calls, the study staff will prompt the subject to report all AEs that have occurred since the last visit. See [Section 12](#) for more details on how AEs are defined, reported, and managed.

7.1.4. Pain Assessments

Numerical Pain Rating Scale (NPRS): This self-administered questionnaire will be conducted using the Study electronic App. This 11-point scale (from 0-10) will ask the patient to assess their pain level over the past 24 hours. This scale will be assessed once each day during screening, baseline and treatment.

Pain Intensity Numerical Rating Scale (PI-NRS): This self-administered questionnaire will be conducted in the clinic. This 11-point scale (from 0-10) will ask the patient to assess their pain level over the past 7 days. This scale will be assessed at visit 1, 2, 4, 6 and 10, or early termination if applicable.

Pain Interference – Short Form 8a (PROMIS): This form is a self-administered questionnaire where subjects will be asked to **measure the effect of pain on their social, cognitive, emotional, physical, and recreational activities** at visit 2, 4, 6 and 10, or early termination if applicable.

Pain Catastrophizing Scale (PCS): Subjects will be asked about their feelings while experiencing or thinking about pain – they don't necessarily have to be in pain while completing this questionnaire. This will be performed at visit 2, 4, 6 and 10, or early termination if applicable.

7.1.5. Sleep Scores

Sleep Disturbance – Short Form 8a (PROMIS): This form is a self-administered questionnaire where subjects will be asked to rate the attributes of their sleep over the past week. A total score is obtained by adding the results of each question (8 in total) to get a score out of 40. This will be assessed in clinic at Visits 2, 4, 6 and 10.

Daily Sleep Interference Scale (DSIS): This self-administered questionnaire is used to quantify sleep interference due to pain. This scale should be completed by patients once a day (upon awakening) to accurately capture variability in sleep interference due to pain. This questionnaire will be conducted using the Study electronic App. This scale will be assessed once each day during screening, baseline and treatment.

7.1.7. Withdrawal/Discontinuation Procedures

A subject may be discontinued from the study at the discretion of the Investigator for medical reasons, or if the subject wishes to withdraw. **Subjects who do not meet the additional criteria for entering the Treatment Period at Visit 2 will be discontinued from the study and considered screen fails.** Women who become pregnant during the study and males whose partners become pregnant during the study will immediately be discontinued from the study. Refer to [Section 12.8](#) for Pregnancy report criteria. Subjects may, at the Investigator’s discretion, also be discontinued at any time due to non-adherence to treatment regimen (e.g., <80% of the doses taken, failed urine drug test) and missed visits. If a subject does not return for a scheduled visit, every effort will be made to contact the subject, and document the subject outcome, if possible.

Based on previous studies of PEA and the FSD201 Phase 1 trial, the most likely AEs would be related to gastrointestinal intolerance and/or diarrhea. Based on this, laboratory changes consistent with severe diarrhea including a decrease in kidney function ($\text{eGFR} < 60 \text{ mL/min/1.73m}^2$) or hyperkalemia/hypokalemia (serum potassium $< 3.0 \text{ mmol/L}$ or serum potassium $> 5.5 \text{ mmol/L}$) will cause the patient to be discontinued from treatment. In addition, patients who experience a single SAE probably related to the study drug will also be discontinued (whether or not this SAE is related to gastrointestinal intolerance/diarrhea). Individual stopping criteria are summarized in Table 3.

Stopping Criteria	Value for Stopping
Kidney Function (eGFR)	<60 mL/min/1.73m ²
Potassium	<3.0 mmol/L or >5.5mmol/L
Development of an SAE probably related to the study drug	1 SAE

Table 3 Individual Stopping Criteria

All subjects who withdraw or are discontinued by the Investigator (for any reason) will have an Early Termination Visit performed within 14 (\pm 2) days of discontinuation or withdrawal. If subjects have ongoing AEs at the time of discontinuation, the site should follow up with the patient until all AEs are resolved or closed.

The study will be stopped if there are four individuals with SAEs probably related to the study drug in the FSD201 treatment group. This represents 10% of the expected 40 patients in the FSD treatment group.

8. Treatment Plan

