11. Female subjects of childbearing potential must use an acceptable method of birth control. Acceptable birth control includes total abstinence from heterosexual intercourse, a vasectomized partner, intrauterine device, or double barrier method including condoms, sponge, diaphragm, contraceptives (oral, parenteral, or transdermal), or vaginal ring with spermicidal jellies or cream. Subjects considered not of childbearing potential must be surgically sterile (total hysterectomy, bilateral salpingo-oophorectomy, or tubal ligation) or be more than one year post-menopausal, defined as a complete cessation of menstruation for at least one year. Male subjects who are sexually active must use an acceptable method of birth control. Acceptable birth control includes total abstinence from heterosexual intercourse, or use of a double barrier method including condoms sponge, diaphragm, contraceptives (oral, parenteral, or transdermal), or vaginal ring with spermicidal jellies or cream used by partner. Periodic abstinence and withdrawal are not acceptable methods of contraception.
12. The subject is in good health as judged by the investigator, based on medical history, physical examination, serum chemistry, hematology, and urine analysis

13. At the screening visit, the body mass index (BMI) is between 18 and 39 kg/m²
14. The subject is sufficiently fluent in English language to answer the questionnaires in clinic and on the App.

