14. Positive urine drug screen for illegal or non-prescribed drugs at the Screening Visit or during the treatment period
15. Pregnant or lactating females or females planning to become pregnant during the study or within 28 days following the last dose of study medication
16. Male patients planning a partner pregnancy or sperm donation during the study or within three months following the last dose of study medication
17. Patients with active malignancy or history of malignancy, except for basal cell or squamous cell carcinoma and actinic keratosis. Basal cell carcinoma and small squamous cell carcinoma of the skin which have been excised according to guidelines within the last 5 years or in situ cervical carcinoma that has been fully treated and shows no evidence of recurrence are allowed
18. Positive human immunodeficiency virus (HIV), hepatitis B or hepatitis C laboratory result
19. Any clinically significant unstable medical abnormality or acute or chronic disease of the cardiovascular, gastrointestinal, respiratory, hepatic, or renal systems. Subject with aspartate transferase or alanine transferase > 2.5 times the upper limit of normal (ULN) or alkaline phosphatase > 3.0 times ULN
20. Any clinically significant deviation from normal in physical examination, vital signs, or clinical laboratory tests, as determined by the investigator
21. Known history of seizure disorder, epilepsy, convulsions, or increased intracranial pressure anytime during the subject's life except for pediatric febrile seizures
22. Subject has received an investigational therapy of any kind within 28 days or 5 half-lives, whichever is longer, before Screening Visit
23. Subject has had known hypersensitivity or intolerance to the use of PEA, diphenhydramine (e.g. Benadryl) or acetaminophen (e.g. Tylenol) and/or their associated formulation components
24. The subject is a member of the site staff or relative of a staff member
25. Individuals with high baseline serum tryptase levels suggestive of Primary or Secondary MCAS (defined as above the normal range of 2.2 to 13.2 µg/L)

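### An eGFR below 60 forces a treatment stop, but entry sets no eGFR limit, so a patient with a stable, mildly low value can be dosed and then stopped without any change

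*Combined protocol and SAP*

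**What the plan says.** **Stopping rule.** Section 7.1.7 names "laboratory changes consistent with severe diarrhea including a decrease in kidney function" and gives limits in parentheses: eGFR <60 mL/min/1.73m², and potassium <3.0 or >5.5 mmol/L. Such values "will cause the patient to be discontinued from treatment". The section then states "Individual stopping criteria are summarized in Table 3". The kidney row of that table is the bare value <60, with no baseline, diarrhea or repeat-test condition.

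**Entry rules.** No inclusion, randomization or exclusion criterion, in sections 10.1 to 10.3 or in the synopsis, gives a number for eGFR, creatinine or potassium. Three criteria bear on renal function:

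- Inclusion 12: "The subject is in good health as judged by the investigator, based on medical history, physical examination, serum chemistry, hematology, and urine analysis".
- Exclusion 19: "Any clinically significant unstable medical abnormality or acute or chronic disease of the cardiovascular, gastrointestinal, respiratory, hepatic, or renal systems". Its only numeric limits are for liver tests: "Subject with aspartate transferase or alanine transferase > 2.5 times the upper limit of normal (ULN) or alkaline phosphatase > 3.0 times ULN".
- Exclusion 20: "Any clinically significant deviation from normal in physical examination, vital signs, or clinical laboratory tests, as determined by the investigator".

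**Laboratory schedule.** Under section 7.1.3, screened patients "will enter the Baseline Period if the results of the laboratory tests confirm their eligibility". Table 2 lists eGFR and potassium at Visit 1 and again at Days 0, 14, 28 and 56. The text below Table 2 lets the investigator repeat laboratory tests at discretion; Table 3 does not refer to this.

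**The concern.** A value that obliges the site to stop treatment does not by itself bar the patient from starting it. The screening laboratory gate exists and the test is done, but the gate has no renal limit to apply. The stopping rule is mandatory while the entry rule is a judgement, so a patient can satisfy the second and already meet the first.

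At stake are exposure to study drug that could have been foreseen as short, a treatment stop that says nothing about the drug, and possibly missing pain scores. In a trial of 60 patients, each early stop has some weight.

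**Working it through.** The plan states no figure for how often the renal rule will trigger, so there is none to reproduce. The check is a comparison of texts, followed by an illustration.

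**1. Entry against stop**

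| | Renal condition | Discretion |
|---|---|---|
| Entry (inclusion 12, exclusions 19 and 20) | good health; renal disease; clinically significant deviation | yes; no number |
| On treatment (section 7.1.7, Table 3) | eGFR <60 | none stated |

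A stable eGFR of 57 in a patient aged up to 75 with no known renal disease can be judged not clinically significant. That patient passes entry and meets Table 3 at the first on-treatment sample.

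**2. Chance of a stop for one such patient**

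Assumptions, none of them in the documents: constant true eGFR *t*, normal and independent measurements, within-person CV of 4% to 8%.

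Single-value probability: p = Φ((60 − t)/(CV × t)).

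*t = 57, judged eligible:*
- p = Φ(3/2.28) = 0.906 at CV 4%; p = Φ(3/4.56) = 0.745 at CV 8%.
- At least one value <60 at Visit 4 or Visit 6: 1 − (1 − p)² = 0.991 to 0.935.
- If a Visit 1 value <60 excluded the patient, entering and then being stopped: (1 − p)[1 − (1 − p)²] = 0.093 to 0.239. Such an exclusion keeps out 75% to 91% of these patients.

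*t = 62:*
- p = Φ(−2/2.48) = 0.210; p = Φ(−2/4.96) = 0.343.
- At least one value <60 at Visit 4 or Visit 6: 0.376 to 0.569.
- If each low value had to be confirmed by a repeat: 1 − (1 − p²)² = 0.086 to 0.222.
- Screened out by a Visit 1 limit of 60: 21% to 34%.

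**3. How many patients**

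The documents give no baseline eGFR distribution. Purely as an illustration, if 0.5% to 5% of enrolled patients were affected, that is 60 × 0.005 = 0.3 to 60 × 0.05 = 3 patients.

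**4. What a stop could cost in data**

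- There are 56/7 = 8 treatment weeks. A stop at Day 14 leaves 2 weekly NPRS means and puts 6 at risk, including the Day 28 week.
- Section 7.1.4 schedules the daily NPRS during screening, baseline and treatment. After a stop, the only clearly scheduled score is at the Early Termination visit (Table 1).
- A stop prompted by the Visit 6 sample comes when the Day 28 week is complete or nearly so. The primary week is therefore at risk mainly from Visit 2 or Visit 4 results.
- Section 14.4 fills missing efficacy data by LOCF. For the responder endpoint with 40 and 20 patients (section 10.5), one patient's filled status moves the response-rate difference by at most 1/40 = 2.5 points (FSD201) or 1/20 = 5 points (placebo).

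**The case against.** The strongest reply is that the governing sentence in section 7.1.7 speaks of changes and a decrease, consistent with severe diarrhea, and that Table 3 only summarises it. On that reading, a stable value without diarrhea triggers nothing. This has weight, but no size of fall is defined anywhere, and the numbers in both the sentence and the table are absolute. A site working from Table 3 would stop the patient.

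The second reply is that entry is already guarded. Inclusion 12 and exclusions 19 and 20 let the investigator refuse such a patient, known chronic kidney disease should fall under exclusion 19, and an investigator who knows Table 3 may well decline an eGFR of 57. This stands, and it is why the case is probably rare. A reader might infer that entry is open to patients with impaired kidneys; the documents do not support that.

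The third reply concerns the consequence. A reader might infer that the Day 28 primary result is lost or biased. The text does not establish this. It says the patient is discontinued from treatment, and a site could continue App entries. The ITT population keeps every randomised patient, the MMRM uses weekly means already collected, and the Early Termination visit includes an NPRS. Nothing suggests that stops for a pre-existing value would differ by arm.

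Finally, an entry limit does not stop patients just above 60 from crossing it by ordinary variation. That is true, and it limits what the fix achieves.

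**Conclusion.** The mismatch is real: the on-treatment renal limit is absolute and mandatory, and entry has no matching number. A patient with a stable, mildly low eGFR judged not clinically significant can be randomised, dosed and stopped without any change in kidney function.

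It is probably rare, and the documents do not allow its frequency to be derived. The per-patient figures (94% to 99% for a true eGFR of 57) apply only once such a patient has been enrolled, and they rest on the assumed CV and independent samples. Loss of the Day 28 week is an inference.

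Two stronger readings should be resisted. One is that potassium has the same gap: it too has no entry number, but the judgement criteria should remove nearly all abnormal values, so little is left to fix. The other is that the absolute limit is wrong and must become a fall from baseline: an absolute floor is a defensible safety choice, and the wording does not show it to be an error.

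This is a cheap improvement worth making and does not threaten the trial's conclusions.

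**What to change.** Add to section 10.3 and to the synopsis an exclusion for Visit 1 eGFR <60 mL/min/1.73m², matching Table 3. Keep the absolute on-treatment limit as a safety floor. For an on-treatment value just under 60 without diarrhea or symptoms, use promptly the repeat already permitted in section 7.1.3. A rule that every low value must be confirmed before stopping would be a safety trade-off and is not proposed. A matching potassium exclusion is optional and adds little.

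Section 7.1 allows enrollment waivers agreed with the sponsor; a waiver of this exclusion would recreate the gap, so none should be given.

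The cost is two lines of text and no new test or visit. There will be a few more screen failures, including some patients truly just above 60 (21% to 34% of those with a true eGFR of 62, under the same CV assumption). Patients just above 60 who do enter can still cross the limit by ordinary variation.

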12.3. Definitions of Adverse Events

Per International Council for Harmonization (ICH) E2A: An adverse event (AE) is any untoward medical occurrence in a patient or clinical investigation subject administered a pharmaceutical product and which does not necessarily have to have a causal relationship with this treatment. An AE can therefore be any unfavourable and unintended sign (including an abnormal laboratory finding, for example), symptom, or disease temporally associated with the use of a medicinal product, whether or not it is considered to be related to the medicinal product.

Medical interventions such as surgeries, diagnostic procedures, and therapeutic procedures are not AEs, but the action taken to treat the medical condition. They should be recorded as treatment of the AEs.

Use the following categories for assigning the certainty of the relatedness:

- **Not Related:** A causal relationship between the study drug and the AE can be easily ruled out (e.g., based on the temporal sequence, absence of a reasonable pathophysiological mechanism, or direct evidence of actual cause).
- **Unlikely Related:** A clinical event, including a laboratory test abnormality, with a temporal relationship to drug administration which makes a causal relationship improbable, and for which other drugs, chemicals, or underlying disease provide plausible explanations.
- **Possibly Related:** A clinical event, including a laboratory test abnormality, with a reasonable time sequence to administration of the drug, but which could also be explained by concurrent disease or other drugs or chemicals. Information on drug withdrawal may be lacking or unclear.
- **Probably Related:** A clinical event, including a laboratory test abnormality, with a reasonable time sequence to administration of the drug, unlikely to be attributed to concurrent disease or other drugs or chemicals, and which follows a clinically reasonable response on withdrawal. Rechallenge information is not required to fulfill this definition.
- **Definitely Related:** A clinical event, including a laboratory test abnormality, which is a known effect of the drug, follows an obvious sequence of time from the drug's administration, and ceases with discontinuation of the drug. Rechallenge information is not required to fulfill this definition.

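### The SAE stopping rules in 7.1.7 name only probably related events and leave out the stronger Definitely Related category; a smaller gap is that no one is assigned to establish the FSD201-arm count

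*Combined protocol and SAP*

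**What the plan says.** Section 7.1.7 states the SAE stop three times, each time with the same causality term.

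- Individual rule: "patients who experience a single SAE probably related to the study drug will also be discontinued".
- Table 3: "Development of an SAE probably related to the study drug", with a stopping value of one SAE.
- Study rule: "The study will be stopped if there are four individuals with SAEs probably related to the study drug in the FSD201 treatment group". The protocol adds that four is 10% of the expected 40 FSD201 patients.

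Section 12.3 gives five relatedness categories: Not, Unlikely, Possibly, Probably and Definitely Related. The last is defined separately, as an event "which is a known effect of the drug, follows an obvious sequence of time from the drug's administration" and that ceases when the drug is stopped.

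On blinding, section 7.1.3 says "The investigators, site staff, monitor and sponsor will be blinded to the study assignment", and then "The study investigators, statistical team, and sponsor will be blinded to the trial randomization code". It describes these releases of the code:

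- a decision by the Principal Investigator in a medical emergency or serious medical condition, for the subject's clinical management;
- pregnancy of a subject or of a subject's partner;
- an optional route under which a subject's "treatment may also be unblinded in the event of a suspected unexpected serious adverse event (SUSAR) in order to determine reportability";
- study-wide release at the end: "Unblinding the treatment assignment for the study will occur after database lock".

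The RTSM code-break function is reserved to the PI. Section 16.4.1 adds sealed envelopes, also for the PI's use.

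**The concern.** The study rule is the only prespecified numeric safety stop at study level. As worded, it responds to the second-strongest causality rating and is silent on the strongest. None of the three statements says *at least probably* or otherwise marks Probably Related as a minimum. A site that follows the text exactly would not have to discontinue a patient whose SAE is rated Definitely Related, and that patient would add nothing to the study count.

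The secondary point concerns operation. A count confined to the FSD201 arm needs treatment codes during the trial. The people who would normally act on it are blinded, and none of the code-break routes is linked to the stop in 7.1.7. The rule is mandatory, but the protocol does not say how anyone learns that it has been met.

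**Working it through.** **Threshold.** Section 10.5 plans 60 patients at 2:1, so the FSD201 arm is 60 × 2/3 = 40, and 4/40 = 10%. The protocol's figure reproduces, and the threshold is not in question.

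**Causality wording, 12.3 against 7.1.7.**

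| Rating in 12.3 | Individual rule and Table 3 | Study count |
|---|---|---|
| Possibly Related | no | no |
| Probably Related | yes | yes |
| Definitely Related | not named | not named |

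Read literally, four definitely related SAEs on FSD201 add 0 to the study count.

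**How often the rule could come into play.** The documents give no SAE rate for this population. Section 4.3 reports no SAEs in a placebo-controlled Phase 1 study of 48 healthy subjects, with repeat dosing for seven days. Even if all 48 had received FSD201, the one-sided 95% upper limit for 0 of 48 is 1 − 0.05^(1/48) = 0.0605, about 6% per patient. Assume a per-patient rate p of a qualifying SAE, equal in both arms:

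| Assumed p | P(Bin(40, p) ≥ 4), FSD201 arm | P(Bin(60, p) ≥ 4), both arms pooled |
|---|---|---|
| 1% | 0.07% | 0.3% |
| 2% | 0.8% | 3.2% |
| 5% | 13.8% | 35% |
| 6% | 21.7% | 49% |

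**What the literal wording could cost.** Suppose a share s of the qualifying SAEs is rated Definitely Related. The literal rule then works at the rate p(1 − s). Both p and s are assumptions; 10% is used because it is the proportion that the threshold represents.

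| Assumed p | Both ratings count | s = 25% | s = 50% | s = 75% |
|---|---|---|---|---|
| 5% | 13.8% | 6.2% | 1.7% | 0.2% |
| 10% | 57.7% | 35.3% | 13.8% | 1.7% |

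This shows direction only. Nothing in the documents supports a particular value of s, and it may well be close to zero.

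**What a blinded pooled count can do.** Four FSD201 cases cannot exist before there are four pooled cases, so a pooled screen set at four cannot trigger late. It cannot settle the rule alone. With 40 and 20 patients and no drug effect, the chance that all four pooled cases are on FSD201 is C(40,4)/C(60,4) = 91,390/487,635 = 18.7%. The chance that at least four are on FSD201 is 45.5% with five pooled cases, 68.6% with six and 92.7% with eight. The pooled count should therefore prompt a code check and should not stop the study by itself.

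**The case against.** The case on the other side is substantial.

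- **Natural reading.** A rule that stops for probable but not for definite causation makes no sense, so most readers would take probable as a minimum. That is very likely the intent. It argues for a short correction rather than for leaving the text, because a safety rule should not rely on sites inferring what was meant.
- **A nearly empty category.** Definitely Related requires a known effect of the drug that ceases on stopping it. Section 4.1 reports more than 3,500 patients given PEA, with no adverse events in most studies. Few SAEs could qualify, and a patient whose SAE does qualify has already come off drug, at least for a time. This stands, and it limits the practical loss, mostly for the individual rule. It does not bring such an event into the study count.
- **Code-break routes exist.** Most related SAEs would probably be unexpected and could reach the SUSAR route. Under 13.1 every SAE goes to the contract research organisation (CRO) within 24 hours. Because the stop is mandatory, the sponsor already has a duty to know whether it is met. All of this stands. What is missing is the operating step. By contrast, 12.8 requires the blind to be broken in pregnancy; 7.1.7 has no matching sentence.
- **The 5% and 6% rows reflect a small Phase 1 study.** They are not evidence of risk. This is correct, and no under-count is claimed.

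A reader might infer that the study stop cannot be operated under the blind, or that definitely related SAEs will in fact be ignored. The documents support neither. The CRO's safety staff and the RTSM provider are not listed among the blinded parties, and a safety or unblinding plan outside these documents may assign the task. Nothing shows that any site would apply the wording literally.

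**Conclusion.** The wording is wrong as it stands, probably through a drafting slip, and should be corrected in all three places. This rests on the text of 7.1.7 and 12.3 alone and on no assumed rate.

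The arm-count gap is real but smaller. The protocol names no one to establish the count, and the code-break routes it describes serve other purposes. That no such arrangement exists anywhere cannot be concluded from these documents.

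Few qualifying events are expected. The probabilities rest on assumed rates, treated as equal in both arms. They show when the rule might be reached and do not measure harm from either gap. Discontinuation by the investigator for medical reasons (7.1.7) and termination by the sponsor at any time (16.4.4) remain as backstops, but both are discretionary.

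**What to change.** 1. In the individual rule, Table 3 and the study rule, write *probably or definitely related*. Keep the threshold of four.
2. Add to 7.1.7: *The CRO keeps a blinded count, pooled over both arms, of individuals with a probably or definitely related SAE. When the count reaches four, and at each further case, a person outside the blinded study team checks the treatment codes and tells the sponsor only whether four are on FSD201.*
3. Amend 7.1.3, which now gives the RTSM code-break function to the PI alone, so that this check is allowed. If a safety or unblinding plan already assigns the task, a cross-reference to it in 7.1.7 would do instead of item 2.

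The cost is a few words in three places, one added provision in 7.1.7 and one conforming sentence in 7.1.3. The code check is needed only if four pooled cases occur. It needs no committee and no new data flow, since the CRO already receives every SAE, and the blinded team stays blinded to individual assignments.
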